SATURATION

(SoutheAsT eUrope microciRculATION) registry

Study protocol version 1.3

Date 03/21/2024

Introduction

Ischemic heart disease is a leading cause of morbidity and mortality. While cardiologists are focused on discrete, visible stenoses of coronary arteries there is increasing awareness of the importance of microcirculation in causing angina. Microvascular bed is comprised of vessels smaller than 500 microns in diameter. Their network is much greater than the network of epicardial vessels and serves important functions such as regulation of myocardial blood flow and cellular metabolism.

Myocardial ischemia is usually caused by significant stenosis of the epicardial coronary artery. However, a study that included over 400000 coronary angiograms found that in over 50% of cases there was no obstructive coronary artery disease (CAD) or stenoses were less than 50%¹. It was not until recently that the importance of coronary microcirculation in causing symptoms and signs of ischemia has been appreciated. Coronary microvascular dysfunction (CMD) has an important effect in determining patient outcomes in a number of clinical settings.

Invasive pressure measurements with coronary wire for measurement of pressure and temperature is a well-established technique in evaluating coronary artery stenoses. Using the same pressure wire, technological advances have allowed estimation of coronary artery flow using principles of thermodilution. This method has been validated in an experimental model, and also in humans, providing an excellent invasive tool in assessing coronary flow reserve (CFR). To assess microcirculation independently, index of microcirculatory resistance (IMR) has been developed. Assuming negligible coronary venous pressure, the resistance of coronary circulation can be calculated as distal coronary pressure (Pd) divided by absolute coronary flow, the latter being proportional to the inverse of mean hyperaemic transit time and thus allowing for calculation of IMR. IMR has been shown to be independent of epicardial coronary artery stenosis. It has been demonstrated that IMR can have predictive value in patients with ST elevation myocardial infarction. A distinct clinical entity known as ischemia with no obstructive coronary arteries (INOCA) has been developed to encompass the patients with clear angina symptoms, but without visible epicardial coronary artery stenoses.

The region of Southeast Europe has its specificities regarding morbidity and mortality from cardiovascular diseases. It includes transitional countries as well as Mediterranean countries where CV diseases are one of the major causes of morbidity. In this registry we wanted to evaluate the practice of patient selection for evaluation of microcirculatory bed, including indications, ischemia tests done, medications prescribed, procedural aspects of microcirculation

evaluation and treatment changes after testing. Also, we want to have an insight regarding adverse cardiovascular events in these patients after invasive coronary physiology.

Aims

Aim 1: To assess the regional practice of patient selection for assessment of invasive coronary physiology including vasospasm testing and estimation of microcirculation by measuring CFR and IMR.

Aim 2: To assess regional procedural aspects of invasive coronary physiology – how aforementioned parameters are measured in the catheterization laboratory

Aim 3: To assess patients' treatment and treatment changes after invasive coronary physiology measurements at each follow up visit.

Aim 4: To compare the cardiovascular outcomes and additional procedures (stress testing, angiography, etc.) done after comprehensive invasive coronary physiology evaluation.

Research design and methods

The study would be prospective, observational and will include patients that underwent invasive coronary physiology with Coroflow Coroventis Cardiovascular System software using Pressure Wire X (Abbott, Abbott Park, IL, US). Participants will undergo routine coronary angiography as well as comprehensive physiologic assessment coronary thermodilution to evaluate for coronary microvascular dysfunction (CMD) and possibly with provocative testing for diagnosis of vasospastic angina (VSA). The study will include centres in Southeast Europe that have obtained Coroventis Coroflow Cardiovascular system and have performed invasive coronary physiology procedures.

Inclusion Criteria

- Adults of both sexes older than 18 years
- Angina symptoms or angina equivalent
- Referred to Cath lab for evaluation of CAD
- Invasive physiology testing performed (microcirculation testing +/- vasospasm testing) using Coroflow Coroventis Cardiovascular system (Abbott, Abbott Park, IL, US)

Exclusion Criteria

- persons under the age of 18
- pregnant or nursing
- no coronary physiology measurements performed

Outcomes

Outcomes will be evaluated every 6 months for 2 years via direct patient contact by research staff or at follow up visits.

- Primary outcomes:
 - o all-cause death and non-fatal MI
 - o composite MACE: all-cause death, non-fatal MI, coronary revascularization, hospitalization for cardiovascular causes (acute coronary syndrome, heart failure, angina, repeated coronary angiography)
- Secondary outcomes: all-cause death, cardiovascular death, MI, coronary revascularization, stroke, hospitalization for heart failure, hospitalization for acute coronary syndrome, repeated coronary angiography
- Patient-centred outcomes
 - o Freedom from angina (SAQ questionnaire)
 - o Quality of life using EQ-5D-5L questionnaire
 - o Follow up non-invasive ischemia testing (if performed)

Study protocol must be approved by the institutional Ethics committee prior to enrolling patients in the study. Patients will be enrolled in the study by the investigators familiar with the study protocol. Patients will be enrolled after invasive coronary physiology procedure. Patients will sign informed consent (IC) form provided and explained by the study team member. After signing IC form patients will be eligible for entering the study. Patients' treatment is responsibility of the treating physician and the participation in the study will not alter patients' treatment.

After enrolling the patients in the study, they will be treated according to local protocols and current recommendations for INOCA.

The patients' data will be stored in an online database managed by Castor EDC organization. Every centre will have the opportunity to access the database and enter patients' data into it. The data collected for a patient in the study will be the following:

Enrollment**1. Demographics**

Date of birth

Date of invasive physiology assessment

Sex

Race

Height

Weight

BMI

Site of enrollment

2. Risk factors

Comorbidities

Recent lab studies

Smoking status

Family history of premature coronary disease

3. Previous cardiovascular events

Myocardial infarction (ever and in the past 30 days)

TIA/stroke

Other cardiovascular diseases

Prior angiographies

Prior PCIs

NYHA class

CCS class

4. Medications**5. Baseline echocardiography****6. Non-invasive ischemia testing****7. Seattle Angina Questionnaire****8. EQ-5D-5L**

9. Coronary angiography findings

Presence of obstructive coronary artery disease (CAD)

Coronary vessel(s) with obstructive CAD

Previous PCI procedure in coronary vessel(s)

10. Invasive physiology procedure

Primary indication

Access site

Radial sheath medications

Withholding the calcium channel blocker, beta blocker, nitrate

Vasospastic angina testing (which artery, what test, result)

Microvascular angina testing (which artery, CFR, IMR, RRR, FFR, Pd, Pa and all transit times)

Complications

Follow up visit

- 1. Demographics**
- 2. Events (MACE)**
- 3. Medications**
- 4. SAQ**
- 5. EQ-5D-5L**
- 6. New non-invasive ischemia testing**

Author correspondence

[name]

Department of interventional cardiology

Cardiology clinic, Institute for cardiovascular diseases Dedinje,

[name]

Email: [contact], [contact]; cell [contact]

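### Must Aim 1 on regional patient selection be changed because the registry holds only patients who were already tested?

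*Protocol*

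**What the plan says.** The first entry under Aims reads "To assess the regional practice of patient selection for assessment of invasive coronary physiology including vasospasm testing", and it goes on to CFR and IMR. The last paragraph of the Introduction states the same purpose more fully: the registry is to "evaluate the practice of patient selection for evaluation of microcirculatory bed, including indications, ischemia tests done, medications prescribed, procedural aspects of microcirculation" evaluation, and then treatment changes after testing.

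Four other places decide who can enter:

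- **Inclusion Criteria:** "Invasive physiology testing performed (microcirculation testing +/- vasospasm testing"), using the named system.
- **Exclusion Criteria:** patients with "no coronary physiology measurements performed".
- **Research design and methods:** "The study will include centres in Southeast Europe that have obtained Coroventis Coroflow Cardiovascular system" and have carried out such procedures.
- **Enrolment text under Outcomes:** "Patients will be enrolled after invasive coronary physiology procedure", and "After signing IC form patients will be eligible for entering the study".

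The variable list opens with "The data collected for a patient in the study will be the following". It includes site of enrolment (item 1), medications (item 4), non-invasive ischemia testing (item 6), presence of obstructive CAD (item 9), and primary indication and vasospasm testing (item 10). It has no entry for patients who were referred and not tested, or tested and not enrolled.

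**The concern.** Selection is a choice among candidates. To learn what drives it, one normally needs both the chosen and the passed over. Here eligibility removes the second group, enrolment comes after the choice has been made, and consent filters the first group further. The word regional also reaches beyond centres that own this system.

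Taken literally, Aim 1 would invite statements about which angina referrals in Southeast Europe are more or less likely to get CFR/IMR testing. A later analysis plan could not rescue such statements, because the untested patients are neither enrolled nor counted. A registry report that made them would have no denominator, and even the direction of a preference could be wrong.

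**Working it through.** **1. Is there a figure to reproduce?** No. The protocol states no sample size, rate, power or testing proportion on this point, so the check is one of what can be identified and of how the passages fit together.

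**2. What the data can identify.** For a patient feature X, Bayes' rule gives

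P(tested | X) = P(X | tested) × P(tested) / P(X).

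The registry estimates P(X | tested), among consenting patients at participating sites. P(tested) and P(X) among all referrals are not collected. The likelihood of testing given X is therefore out of reach, while the profile of tested patients is not.

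**3. An illustration with assumed inputs.** Let s be the share without obstructive CAD among registered patients, and p the same share among all angina referrals at those sites. The protocol gives neither. The ratio of testing rates, without versus with obstructive CAD, is [s/(1−s)] / [p/(1−p)].

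Odds of p: 0.50/0.50 = 1.00; 0.70/0.30 = 2.33; 0.90/0.10 = 9.00.

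| s (odds) | p = 50% | p = 70% | p = 90% |
|---|---|---|---|
| 90% (9.00) | 9.00/1.00 = 9.0 | 9.00/2.33 = 3.9 | 9.00/9.00 = 1.0 |
| 80% (4.00) | 4.00/1.00 = 4.0 | 4.00/2.33 = 1.7 | 4.00/9.00 = 0.44 |
| 70% (2.33) | 2.33/1.00 = 2.3 | 2.33/2.33 = 1.0 | 2.33/9.00 = 0.26 |

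The spread from 0.26 to 9.0 is a product of the chosen grid. It shows that the ratio needs a denominator and says nothing about this registry in particular. The Introduction's figure of over 50% cannot stand in for p: it comes from an outside angiogram series and also counts stenoses below 50%.

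**4. What the protocol sets out to learn.** The Introduction's purpose statement can be set beside the Aims and the data list:

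| Introduction | Aim it matches | Where collected |
|---|---|---|
| Indications | Aim 1 | Item 10, primary indication |
| Ischemia tests done | Aim 1 | Item 6 |
| Medications prescribed | Aim 1 | Item 4 |
| Procedural aspects | Aim 2 | Item 10 |
| Treatment changes after testing | Aim 3 | Medications at follow-up |
| Adverse events (next sentence) | Aim 4 | Events at follow-up |

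The statement runs in the order of the four aims. On that reading its first three items are the content of Aim 1, and each is a property of a tested patient that the registry records.

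**5. Is the unidentifiable quantity proposed anywhere?** No aim or outcome mentions a testing rate, a probability of being tested, or a comparison of tested with untested patients.

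**6. Vasospasm testing.** Microcirculation testing is required for entry, but vasospasm testing is optional and recorded. Which registered patients also had provocation can therefore be described directly, so this part of Aim 1 has its comparison group inside the registry, within the microcirculation-tested population.

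**The case for a change.** The strongest case for a change is that Aim 1 itself carries no limit. The Introduction's list runs on from indications to procedural aspects and treatment changes, which happen during or after the test and cannot be reasons for choosing a patient. It can therefore be argued that the list does not define selection at all, and that one clearer sentence would cost almost nothing and would stop an aim from promising more than the design can give. Timing adds some weight: untested patients who are not counted during enrolment may be hard to reconstruct later.

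Part of this stands. The wording is broader than the data, in respect of both selection and region, and the likelihood of CFR/IMR testing relative to untested referrals cannot be estimated by any analysis. The argument from the list is weaker, because the later items correspond to Aims 2 and 3 and so leave the first three as the natural content of Aim 1. The centre restriction is stated openly in the section right after the Aims, and Aim 2 uses regional in the same way, so a reader is not misled about which centres contribute. The timing point matters only if a claim about untested patients is wanted, and the protocol makes none.

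**Conclusion.** No change to the plan follows. Aim 1 is loosely worded, but analysts following the protocol would tabulate indications, prior ischemia tests, medications and patient characteristics, together with the use of vasospasm provocation. Those are sound descriptive results for consenting, tested patients at participating centres. A reworded aim would lead to the same tables from the same variables.

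The larger remedy, a count at each site of angina patients at angiography without physiology and of tested patients not enrolled, would need site time, a protocol amendment and ethics committee approval. It would serve only an inference that the protocol does not propose. Adding an objective on correlates of vasospasm provocation would be a new aim and is not needed as a correction.

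No size can be put on the issue from the protocol; the range of 0.26 to 9.0 rests wholly on assumed shares and should carry no weight. The conclusion depends on reading Aim 1 in line with the Introduction, and on reports saying plainly that nothing is inferred about untested referrals or about centres without the system. If the sponsor did mean to claim who is preferentially chosen for CFR/IMR testing, the design could not support it.

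### Obstructive CAD is eligible, but the data list has no item for index-session or already-planned PCI, and the composite MACE counts revascularization with no time zero or exception for planned procedures

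*Protocol*

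**What the plan says.** **Who is eligible.** The protocol's inclusion criteria require angina or an equivalent, physiology testing, and that the patient was "Referred to Cath lab for evaluation of CAD". The exclusions are age under 18, pregnancy or nursing, and "no coronary physiology measurements performed". Neither obstructive disease nor PCI in the same session excludes a patient. Item 9 of the enrolment data lists "Presence of obstructive coronary artery disease (CAD" and the vessels affected.

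**What is collected.** The list opens with "The data collected for a patient in the study will be the following". PCI appears in it twice, both times as history: prior PCIs in item 3 and "Previous PCI procedure in coronary vessel(s" in item 9. Item 10, on the index procedure, covers indication, access, sheath medications, withheld drugs, vasospasm testing, complications and "Microvascular angina testing (which artery, CFR, IMR, RRR, FFR, Pd, Pa and all transit times". The follow-up form lists MACE events, medications, questionnaires and new ischemia tests.

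**Timing and use.** "Patients will be enrolled after invasive coronary physiology procedure". Aim 3 concerns treatment and "treatment changes after invasive coronary physiology measurements at each follow up visit". Aim 4 compares outcomes and additional procedures after the physiology evaluation. The composite MACE includes coronary revascularization without qualification, and also admissions for repeat angiography.

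**The concern.** A PCI done in the index session has no clear place in this structure. It is not plainly history, because it belongs to the procedure that qualifies the patient. It is not plainly a follow-up event either, because no start of follow-up is defined. A PCI decided in that session but done later does fit the follow-up form, where it counts as an adverse event although it was part of the initial treatment plan.

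Three things are at stake:

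- **The composite primary outcome.** In patients with obstructive CAD it would partly reflect the baseline angiogram and local habits on staging, which weakens the comparison in Aim 4.
- **Aim 3.** It may miss revascularization as a treatment in these patients.
- **The physiology values.** If some sets were measured after PCI, nothing in the list would identify them.

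An SAP can set counting rules and group measurements, but only on variables that were collected. The gap in the data items therefore has to be closed in the protocol or the case report form.

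**Working it through.** The protocol gives no sample size, event rate or PCI rate, so there is no figure of its own to reproduce. The check is a reading of the data list, followed by an illustration on assumed inputs.

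**Step 1: count the items.**

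| Subject | Items listed |
|---|---|
| PCI before the index procedure | 2 (items 3 and 9) |
| PCI in the index session | 0 |
| Physiology taken before or after PCI | 0 |
| Revascularization already planned at the index session | 0 |
| Follow-up items that include revascularization | 1 (MACE events) |

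**Step 2: follow each kind of PCI through the plan as written.**

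- *Index-session PCI.* Enrolment follows the procedure, and prior and previous have no stated reference point. A site may enter the PCI as previous (it precedes enrolment), report it as MACE (it is a revascularization, and if it follows the physiology it also falls after the starting point named in Aim 4), or leave it out. All three are defensible readings.
- *Staged PCI decided at the index session.* It takes place within the two years of follow-up and is a coronary revascularization, so it meets the composite as written. If the patient is admitted for it, it may also qualify through the repeat-angiography component.
- *The other primary outcome.* Death and non-fatal MI contains no revascularization, so this counting problem does not touch it.

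**Step 3: illustrate the staged-PCI effect.** Every input is an assumption; none comes from the documents.

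- b = 12%: two-year MACE from other causes
- o = 20% to 40%: share with obstructive CAD
- s = 10% to 20%: share of those with a staged PCI, taken as independent of other events

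Observed MACE = 1 − (1 − b)(1 − o·s)

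| o | s | Calculation | MACE |
|---|---|---|---|
| 20% | 10% | 1 − 0.88 × 0.98 | 13.8% |
| 30% | 20% | 1 − 0.88 × 0.94 | 17.3% |
| 40% | 20% | 1 − 0.88 × 0.92 | 19.0% |

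The excess is (1 − b)·o·s, or 1.8 to 7.0 percentage points here. Whatever b is, it cannot exceed o·s, which is 2 to 8 points over these ranges. It goes to zero with o.

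By construction the excess lies wholly in the obstructive group. There MACE would be 1 − 0.88 × 0.90 = 20.8% at s = 10% and 1 − 0.88 × 0.80 = 29.6% at s = 20%, against 12% in the rest.

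**The case against.** The strongest reply is that the list consists largely of headings, not of case-report-form fields. Medications, comorbidities and MACE events are not itemised either, so a missing sub-item does not prove that the database lacks it. The rationale centres on microvascular disease, and the protocol expects treatment in line with INOCA recommendations, so the affected subgroup may be small. Event-counting rules often sit in an SAP, which is not at hand.

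Much of this stands, and it rules out four stronger conclusions that a reader might draw:

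- *That index PCI is recorded nowhere.* The text shows only that no dedicated item is listed. A site could still enter it as previous or as an event.
- *That the registry misses the main treatment.* Medications are collected at enrolment and at follow-up. PCI could be the main treatment only in patients with obstructive disease who had it, and their number is not given.
- *That physiology from before and after PCI is in fact pooled.* No section says that post-PCI measurements are taken or combined. The Introduction also calls IMR independent of epicardial stenosis, so the concern bears more on CFR and FFR.
- *That nothing can be recovered.* The vessel with obstructive disease, the artery tested, FFR, the pressures and the date of the physiology assessment are listed. They allow partial stratification, and event dates, if collected, would help to separate early procedures.

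The reply does not remove the ambiguity. The list is presented as the data to be collected, and item 10 goes into as much detail as sheath medications and transit times without mentioning PCI. No later analysis rule can separate planned from unplanned revascularization if sites were never asked.

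**Conclusion.** The concern holds in a limited form. Obstructive CAD is eligible, three facts about revascularization at the index session have no listed item, and the composite has neither a time zero nor an exception for planned procedures. How an index PCI is recorded is left to the site, and a staged PCI decided at the index angiogram counts as a primary-outcome event.

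The size cannot be derived from the documents. The range of 13.8% to 19.0% against an assumed 12% shows only what moderate shares would do; with few obstructive patients the effect is negligible. The defect itself follows from the text and does not depend on those figures. It is confined to patients with obstructive CAD, to the composite and the secondary outcomes on revascularization and repeat angiography, and to what Aim 3 can report on treatment.

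**What to change.** 1. **Add three items to sections 9 and 10 of the enrolment data:** PCI in the index session (yes/no, vessel); a before-PCI or after-PCI flag for each physiology set; further revascularization already planned at the end of the session (yes/no).
2. **State the time zero** for all events as the end of the index procedure.
3. **State the counting rule.** Index-session and already-planned revascularization is reported as treatment under Aim 3 and does not count as MACE. The rule should also cover an admission or repeat angiogram that takes place only to carry out the planned procedure; otherwise the same PCI re-enters through the hospitalization component.
4. **Do not pool** pre-PCI and post-PCI physiology values where both occur.

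These changes affect recording and outcome definition only, not patient care. The cost is three fields that should be available from the procedure report and a few sentences in the protocol. MACE events will be slightly fewer. If enrolment has started, which the protocol does not say, some back-filling is needed, and the planned-revascularization item will be the hardest to complete in retrospect.
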